8.2. Treatment Assignment

Potential study subjects will include “all-comers” who meet the enrollment criteria. Study Investigators are expected to approach all potentially eligible study subjects who have been implanted (between 1 and 21 calendar days post CRT-D device implant window) with an

eligible BSC CRT-D device and a compatible quadripolar LV lead according to their corresponding Physician Technical Manual

8.2.1. Treatment and Control

Subjects will not be randomized or blinded to treatment received. Any subject meeting all inclusion and no exclusion criteria is enrollment eligible for the SMART Registry. Subjects are considered enrolled in the study once the informed consent form (ICF) has been executed.

8.3. Justification for the Study Design

While a randomized study is considered the gold standard in many clinical research settings, considering the sample size and study objectives, a non-randomized, observational study with up to 2000 subjects is considered appropriate to meet the objectives of the study. In order to obtain a “real world” picture of the device use, inclusion and exclusion criteria and follow up schedule has been written generally enough to allow for study center specific standard of practice that should accurately capture the device use in a “standard” clinical setting.

Additionally by requiring the study centers to follow their specific standard of practice, risk to the subject is minimized because the treatment received by the subject will be similar to the treatment the subject would receive if not participating in the study.

The SMART Registry is a global, multicenter, prospective, observational, single-arm post market study (registry), including a European, multicenter, prospective, single-arm sub-study (NG4 PMCF). The objective of the SMART Registry is to characterize rates of CRT response in a general CRT-D population as well as in selected subgroups defined by device and subject characteristics.

It is desired to have a high degree of confidence in the CRT response rates obtained in the study. To obtain a two-sided 95% confidence interval width of the CRT response rate that does not exceed 5%, a total of 2000 subject enrollments are required. Additionally, it is expected that with a total of 2000 enrollments, each subgroup analysis will include approximately 50 subjects.

A minimum of 103 NG4 PMCF subjects are required to sufficiently power the PMCF endpoint.

The primary objective of the NG4 PMCF sub-study is to gather data to establish the chronic safety, performance and effectiveness of NG4 CRT-D devices.

9. Subject Selection

9.1. Study Population and Eligibility

Subjects included in the SMART Registry should be selected from the investigator’s general patient population of subjects who are indicated for CRT-D implantation per BSC labeled

indication provided in **Section 9.2**. Investigators are responsible for screening all potential subjects and selecting those who meet the eligibility criteria for the study as described in **Sections 9.2** and **Section 9.3** below. Investigators are encouraged to include *consecutive* subjects in order to minimize selection biases.

9.2. Inclusion Criteria

Subjects who meet all of the following criteria (see Table 9.2-1) may be given consideration for inclusion in this Registry, provided no exclusion criterion (see Section 9.3) is met.

Table 9.2-1: Inclusion Criteria

Clinical Inclusion Criteria	
• Subject implanted or upgraded with an NG3 or NG4 CRT-D device based on BSC labelling for devices in specific geographies in conjunction with a quadripolar LV lead from any manufacturer• Subjects must be enrolled between 1 and 21 calendar days post CRT-D implantation procedure• Subject is age 18 or above, or of legal age and willing and capable to provide informed consent specific to each country and national laws• Subject is willing and capable of providing informed consent• Subject is willing and capable of complying with follow-up visits and procedures as defined by this protocol
------------------------------------	--

9.3. Exclusion Criteria

Subjects who meet any one of the following criteria (Table 9.3-1) will be excluded from this clinical study.

Table 9.3-1: Exclusion Criteria

Clinical Exclusion Criteria	
• Subject with documented life expectancy of less than 12 months• Subject currently on the active heart transplant list or has a current Left Ventricular Assist Device or other assist device.• Subject who have had a pre-existing CRT device• Subject Enrolled in any other concurrent clinical trial without prior written approval from BSC Clinical Trial Manager• Women of childbearing potential who are or might be pregnant at time of study enrolment• Any contra-indication to receive a CRT-D device per local guidelines
------------------------------------	---

10. Subject Accountability

10.1. Point of Enrollment

Investigators will select subjects who are appropriate for study inclusion as per eligibility criteria. Subjects who meet the eligibility criteria and agree to participate will be given written informed consent approved by the center's Institutional Review Board (IRB) / Ethics Review Committee (ERC).

All subjects who complete the informed consent process, sign and date the informed consent form (ICF) are considered enrolled in the SMART Registry. Subjects who have signed the informed consent but are found to not meet eligibility criteria at the time of enrollment are classified as consent ineligible. No study related procedures or data collection can take place until the ICF is executed. Screening tests that are part of Standard of Care (SOC) can be used to determine pre-eligibility. Subjects enrolled in this registry must be followed per this protocol.

Subjects will be enrolled at post implant (between 1 and 21 calendar days post CRT-D implantation procedure).

SMART Registry subject is considered as part of the NG4 PMCF Cohort when enrolled in a European site, has an NG4 device implanted and LV MSP feature is enabled.

10.2. Withdrawal

All subjects enrolled in the clinical study (including those withdrawn from the clinical study or lost to follow-up) shall be accounted for and documented. If a subject withdraws from this registry, the reason(s) shall be reported. If such withdrawal is due to problems related to device safety or performance, the investigator shall ask for the subject's permission to follow his/her status/condition outside of the clinical study.

Reasons for withdrawal include, but are not limited to:

- Subject found not to meet eligibility criteria
- Subject choice to withdraw consent
- PI decision to withdraw the subject
- Device explanted and not replaced with an NG3/NG4 CRT-D system
- Implanted system element not active (IPG, RA lead, RV lead and quadripolar LV lead)
- Use of epicardial lead
- Ventricular Assist Device insertion or heart transplant
- Lost to follow-up, despite best efforts to locate the subject;
 - Three documented attempts to contact the subject are required to declare a subject lost to follow up.
- Death (see Section 19.7 for reporting requirements)

If a subject withdraws from the clinical investigation, the reason(s) shall be reported on the corresponding eCRF of the EDC system. Data up to the point of withdrawal will be collected and may be used. All open adverse events should be closed or documented as chronic.

10.3. *Subject Status and Classification*

Enrolled Subjects will be classified in the study as follows:

- Consented and ineligible - A study subject who has signed informed consent form (ICF) but is found to not meet eligibility criteria will be considered a consent ineligible subject and will not count towards the enrollment ceiling. There are no follow-up or adverse event reporting requirements for consent ineligible subjects. The original signed ICF must be maintained in the center's administrative file.
- Actively Enrolled (Consented and eligible) - subjects who have signed the ICF, meet all inclusion criteria and do not meet any of the exclusion criteria. These subjects will be followed in accordance with Clinical Investigational Plan (CIP) follow up schedule and included in the future study analysis. The original signed ICF must be maintained in the center's administrative file. All applicable case report forms per the CIP must be completed.
- NG4 PMCF Cohort - will be a minimum of the first 103 European subjects identified by the Sponsor enrolled in the SMART Registry, implanted with an NG4 device and that had LV MultiSite feature enabled at any time during the initial 12 months follow up.

10.4. *Enrollment Controls*

Approximately 2000 subjects will be enrolled in the SMART Registry. Study sites will be notified when the enrollment is complete. No single site shall enroll more than 20% subjects to mitigate any bias from a single center in final study analysis without the prior written approval from BSC Clinical Trial Manager.

NG4 PMCF Cohort will be completed as soon as a minimum of the first 103 European subjects identified by the Sponsor enrolled in the SMART Registry, implanted with an NG4 device and that had LV MultiSite feature enabled at any time during the initial 12 months follow up.

Once the NG4 PMCF Cohort has been completed, a notification will be submitted to all European sites confirming that no additional subjects are required to be identified to be followed more than 12 months.

11. Study Methods

11.1. *Data Collection*

The data collection schedule is shown in Table 11.1-1.

SMART Registry subjects:

- Enrollment and consenting visit at Post-Implant (between 1 and 21 calendar days after CRT-D implantation procedure) *(Required)*
- 12 months Clinic Visit (330-390 calendar days from enrollment date) *(Required)*
- Additional Standard of Care (SOC) Visits

NG4 PMCF Cohort: Only for the identified NG4 PMCF Cohort:

In addition to complete all standard SMART Registry Clinic Visits stated above, NG4 PMCF subjects will have to complete the following Clinic Visits:

- 24 months Clinic Visit (690-750 calendar days from enrollment date) *(Required)*
- 36 months Clinic Visit (1050-1110 calendar days from enrollment date) *(Required)*
- Annual Follow-Up Visit after 36 months and until last PMCF subject will complete the 36 months Clinic Visit *(Required)*

Table 11.1-1: Data Collection Schedule						
Procedure/Assessment	SMART Registry			Only NG4 PMCF subjects (in addition to the standard SMART Registry)		
	Enrollment visit (Index Visit) (between 1 and 21 days post CRT-D implantation procedure)	12 months Clinic Visit (330 days - 390 days post-enrollment)	Additional SOC Clinic Visit (only if per site SOC)	24 months Clinic Visit (690 days - 750 days post-enrollment)	36 months Clinic Visit (1050 days - 1110 days post-enrollment)	Annual Clinic Visit (until last PMCF subject will achieve 36 months of follow up)
Informed consent process, including informed consent signature date	X	--	--	--	--	--
Inclusion/Exclusion	X	--	--	--	--	--
Demographics	X	--	--	--	--	--
Physical assessment	X	X	O	--	--	--
Medical history	X	--	--	--	--	--
Echo data post implant (if available)	X	X	O	--	--	--
NYHA Class	X	X	O	X	X	X
ECG Data (if available)	X	X	O	--	--	--
Patient & Physician Global Assessments (Global Assessment Tool)	--	X	--	--	--	--
Cardiac Medications	X	X*	O*	X*	X*	X*
Implanted system information	X	X**	X**	X**	X**	X**
Device Initial interrogation, settings and status and print of Combined Report and Settings Report	X	X	X	X	X	X
Leads measurements	X	X	O	X	X	X
Optimization information as per site SOC	X	X	X	X	X	X
Device Final Combined Report and Setting Report						
Adverse Event Assessment	X	X	X	X	X	X

X = required; O = optional; -- = not required, * = Need to document changes to cardiac meds only (new, increase, decrease), ** = Need to document only if there is changes from implanted system
NYHA = New York Heart Association; ECG = Electrocardiogram; HF = Heart Failure, SOC – Standard of Care

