11.5.6.3. CCS Status Classification

Subjects will be classified as improved, unchanged, or worsened by comparing their clinical response in the current visit to their enrollment visit. At the 12 months Clinic Visit, subjects' status will be compared to their status at enrollment. The following criteria will be used:

- Improved: Subjects are considered improved if they experienced a favorable change in at least one NYHA functional class or in the PGA (or both) while remaining alive and free of HF hospitalization comparing to their status in the Enrollment Visit. See Table 11.5-1 on selecting improved PGA status.

- Worsened: Subjects are considered worsened if any of the followings occurs:
 - died (from any cause) or
 - experienced an HF hospitalization or
 - reported worsening of at least one NYHA functional class or
 - reported worsening of the PGA comparing to their status immediately prior to receiving the CRT-D implantation. See Table 11.5-1 on selecting worsened PGA status.

- Unchanged: Subjects are considered unchanged if they are neither improved nor worsened.

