12.2.1. Analysis Sets

All subjects with complete Clinical Composite Score data at 12 months will contribute to the analyses evaluating CRT Response rates. All subjects in the NG4 PMCF Cohort will contribute data to the PMCF Primary Endpoint.

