12.3.3. Subgroup Analyses

The list of baseline covariates (with applicable subgroups in parentheses) includes, but is not necessarily limited to:

- Ischemic Etiology (Ischemic vs Non-Ischemic)
- Bundle Branch Block morphology (LBBB vs Non-LBBB)
- NYHA class (I/II vs III/IV)
- Presence of atrial fibrillation (Yes or No)
- Diabetes (Yes vs. No)
- Sex (Male vs. Female)
- Age < 65 years vs. ≥ 65 years
- RV-LV electrical delay (< 70 ms vs. ≥ 70 ms)
- QRS-LV at the implantation site
- QRS width (< 150 ms vs. ≥ 150 ms)

CRT Response rates (Full Registry) and PG-related complication-free rates (NG PMCF Cohort) will be compared between the two subgroups for each covariate. A Cochran-Armitage test for trend will be performed to compare CRT Response rates across subgroups. A log-rank test will be used to compare PG-related complication-free rates across subgroups. Additional cutpoints may be evaluated for continuous covariates, based on the data and/or clinical determination.

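### Section 10.2 lets sites withdraw subjects after a device or therapy change, and those with no earlier death or HF hospitalization then leave the 12-month response denominator

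*Combined protocol and SAP*

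**What the plan says.** Section 10.2 opens its list with "Reasons for withdrawal include, but are not limited to". Besides withdrawn consent, ineligibility, loss to follow-up and death, the list names an explanted device not replaced by an NG3/NG4 system, "Implanted system element not active (IPG, RA lead, RV lead and quadripolar LV lead"), "Use of epicardial lead" and "Ventricular Assist Device insertion or heart transplant". It adds that data up to withdrawal are collected and may be used. Where withdrawal is due to device safety or performance, later follow-up needs the subject's permission and takes place outside the study.

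Section 12.2.1 defines the response analysis set: "All subjects with complete Clinical Composite Score data at 12 months will contribute to the analyses evaluating CRT Response rates". It does not define complete data. Section 12 gives no missing-data rule and no sensitivity analysis for response.

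Under Section 11.5.6.3, Worsened subjects are those who died, "experienced an HF hospitalization or" reported a worse NYHA class or PGA. VAD, transplant, explant and loss of LV pacing are not named.

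Table 11.1-1 requires the PGA at the 12-month visit and at no other visit. NYHA class is optional at additional standard-of-care visits.

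**The concern.** The listed device and rescue events are things that happen to the therapy. They are not loss of contact or refusal to continue. A subject whose LV lead is inactive, or whose system has been explanted, no longer receives the therapy as planned and may well be less likely to improve. If follow-up ends at that point and the analysis keeps only completers, the denominator is enriched for subjects whose therapy continued.

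The primary objective is the response rate in a general CRT-D population (Section 6), and Section 8.2 describes the subjects as all-comers. A rate among subjects whose system stayed intact answers a narrower question, and enrolling more subjects does not remove the difference. Because sites may differ in when they withdraw a subject, the practice can also vary between sites.

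**Working it through.** **Step 1: can a withdrawn subject be scored?** Take a subject withdrawn at, say, month 6.

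- If the subject died, or had an HF hospitalization first, a Worsened criterion is already met. Section 12.2.1 does not say that this makes the CCS complete when PGA and 12-month NYHA are missing.
- If neither occurred, no PGA exists, because the only scheduled one is at 12 months, and a later NYHA class may not exist either. Permission to use earlier data cannot supply these components, so there is no CCS.

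**Step 2: which events fall into the gap?**

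- *Explant, inactive LV lead, epicardial lead.* None is a CCS component and none needs an HF admission. The gap is firmest here.
- *VAD or transplant.* Section 11.5.6.1 counts any event with HF as primary cause and an admission spanning a date change. Many of these subjects would already be Worsened, so the gap is smaller.
- *Inactive RA lead.* Section 9.2 requires an LV lead but mentions no RA lead, and Section 8.2.1 says "Any subject meeting all inclusion and no exclusion criteria is enrollment eligible for the SMART Registry". An effect on subjects with atrial fibrillation is possible but cannot be sized.

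**Step 3: the plan's own precision figure.** Section 12.1.2.2 asks for 2000 enrollments so that the 95% interval is at most 5 points wide, a half-width of 2.5 points. At p = 0.5, n = (2 × 1.96 × 0.5 / 0.05)² = 1537, so 2000 is not reproduced but is conservative. The width is 4.38 points at n = 2000 and 4.75 at n = 1700. Lost numbers are therefore not the problem.

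**Step 4: size of the bias.** Response is taken as Improved. The Introduction gives about two-thirds for Class III-IV and about 10 points less for Class I-II; 50% is added as a lower bound. The withdrawn share w is an assumption, because the documents give none. The 15% annual attrition in Section 12.1.3.3 is for the PMCF cohort and covers all causes.

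If none of the withdrawn improved, completer rate = π / (1 − w) and bias = π / (1 − w) − π.

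| w (assumed) | Completer rate, π = 66.7% | Bias, π = 66.7% | Bias, π = 50% |
|---|---|---|---|
| 1% | 67.3% | +0.7 | +0.5 |
| 3% | 68.7% | +2.1 | +1.5 |
| 5% | 70.2% | +3.5 | +2.6 |
| 10% | 74.1% | +7.4 | +5.6 |

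The bias equals 2.5 points when w = 0.025 / (π + 0.025). This is 0.025 / 0.6917 = 3.6% (about 72 of 2000) at π = 2/3, and 0.025 / 0.525 = 4.8% (about 95 of 2000) at π = 50%.

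If a fraction q of the withdrawn improved and the completer rate is c, bias = w(c − q). With c = 66.7% and w = 5%:

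- q = 0: 0.05 × 0.667 = 3.3 points
- q = 20%: 0.05 × 0.467 = 2.3 points
- q = 40%: 0.05 × 0.267 = 1.3 points

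**The case against.** **Withdrawal is not mandatory.** A reader might infer that each listed event removes the subject. The list is open, sits alongside investigator decision, and does not say that an event ends follow-up. This stands: the text permits withdrawal and does not compel it.

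**Withdrawn is not the same as uncounted.** Death is on the same list, yet it scores Worsened. Section 10.3 says that actively enrolled subjects are included in the analysis. This is right for subjects with a prior death or HF hospitalization, provided that complete is read generously. It does not help the others, and the statement in 10.3 conflicts with 12.2.1 for them.

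**VAD and transplant.** A reader might infer that these subjects escape, for example through a planned admission. Section 11.5.6.1 has no exemption for planned admissions; that exemption belongs to the serious adverse event definition in Table 19.2-1. Section 9.3 also excludes subjects on the active transplant list or with a current assist device, which should limit numbers. This stands, and the point is correspondingly weaker here.

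**Atrial fibrillation.** A reader might infer that AF subjects drop out through the RA-lead item and that the planned subgroup, "Presence of atrial fibrillation (Yes or No", is distorted. The documents do not support this. AF is not a withdrawal reason, nothing links an inactive RA lead to AF, and an item about an implanted element does not clearly reach a lead that was never implanted.

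**Selection on outcome.** The Introduction names poor lead location and AF as possible reasons for non-response. A badly placed but active lead is not on the list, and an epicardial or inactive lead does not prove non-response. The link to outcome is plausible but not shown.

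**Exploratory registry.** There is no formal hypothesis, so no test decision is at risk. The response rate is nevertheless the primary endpoint, and its accuracy is what the sample size is meant to secure.

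**Conclusion.** The point holds as a gap in handling. As written, the plan allows withdrawal for events that may be related to response, collects the PGA too late to score those subjects, and analyses completers only. It does not say how they enter the CCS. The likely direction is upward. The gap is firmest for explant and for inactive or epicardial LV leads, and smaller for VAD and transplant. For AF it is only a possibility.

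The size cannot be derived from the documents. An assumed 5% withdrawn gives +3.5 points when the true rate is two-thirds and none improved, and about +1.3 points when the completer rate is 66.7% and 40% of the withdrawn improved. These figures count only withdrawals that have no Worsened event already on record. Confidence is medium. It is a cheap improvement worth making, and it does not invalidate the registry.

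**What to change.** 1. **Section 10.2.** Record explant, inactive system element, epicardial lead, and VAD or transplant as dated treatment changes. Keep consenting subjects in follow-up for 12-month NYHA class, PGA, vital status and HF events. This concerns data collection only and leaves clinical care unchanged.
2. **Section 12.2.1.** Define complete CCS data so that any Worsened event before 12 months is sufficient, and reconcile the section with the statement in 10.3 that actively enrolled subjects are analysed.
3. **Sensitivity analysis.** Repeat the response rate with subjects withdrawn for these reasons, including VAD and transplant, counted as not improved. Report the number withdrawn for each reason. The Worsened definition of the published score then need not change.

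The cost is protocol wording, one eCRF flag and a few more 12-month visits, which the protocol already requires of enrolled subjects. The reported response rate may be slightly lower.

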11.2. Study Candidate Screening

After approval by the investigator's IRB/EC and the sponsor or delegated representative the investigator or designee is responsible for screening potential subjects and selecting those who meet all inclusion criteria and do not meet any of exclusion criteria. A formal screening log is not required to be maintained.

11.3. Informed Consent

Subjects who meet all of the inclusion criteria, none of the exclusion criteria, and undergo the informed consent process, sign, and date the informed consent form are considered enrolled in the study. No data collection, data entry, or study specific procedure shall be performed prior to having appropriately consented the subject.

11.4. Enrollment Visit - Index Visit (Day 0)

The Enrollment Visit may occur at pre-discharge of CRT-D implantation procedure but only between 1 and 21 calendar days post CRT-D implantation procedure. Enrollment cannot occur on the same day of the implantation procedure.

An overview of data to be collected at the Enrollment Visit is provided below, with further details followed in the sections below.

- Inclusion and Exclusion (including CRT-D indication verification according BSC labelling)
- Subject demographics
- Subject Physical Assessment
- Medical history
- NYHA Class Assessment
- Cardiac medications
- Implanted system information (CRT-D IPG, RA lead, RV lead and LV lead information including LV lead location)
- Device Initial Interrogation to capture current settings, programming and status (including battery consumption) at the beginning of the Clinic Visit
- Lead measurements
- BSC Optimization features data: SmartDelay test and value (if done), LV Vector Guide test and value (if done), LV MSP (if enabled), SmartVector and SmartOffset value (if done), HeartLogic information (if applicable) and other optimization methods as per site SOC

- Device Final Report to capture programming, settings, programming and status (including battery consumption) at the end of the Clinic Visit before subject will leave the site.
- Adverse event assessment

